## 3. Objectives

### 3.1 Primary objective

The primary objective of this study is to explore the diagnostic accuracy of MRDTI in the diagnostic management of acute and chronic SVT in a prospective diagnostic proof of concept study.

### 3.2 Secondary objectives

The secondary objectives of this study are:

- 1) To optimise MRDTI sequences for imaging of SVT
- 2) To assess the interobserver agreement of the readers of MRDTI for suspected SVT

## 4. Methods

### 4.1 Study design

This study is a prospective diagnostic proof of concept study to explore the diagnostic accuracy of MRDTI in the diagnostic management of acute and chronic SVT. This will be achieved by performing MRDTI scans to adjust and optimize the DTI scan sequence in 3-5 patients with confirmed, symptomatic SVT. If a reproducible clearly positive DTI signal is achieved in all patients, the study can proceed with the inclusion of cohort 1 and 2, i.e. 35 patients with confirmed acute SVT (cases) and in 35 patients with confirmed, non-symptomatic chronic SVT (controls). All scans will be evaluated post-hoc by expert readers blinded for the final diagnosis. It is predetermined that at least five patients of each SVT site (PVT, SpVT and BCS) and at least five patients of each SVT risk factor (oncologic, post-surgical and inflammatoir/infectious) will be included. To make sure that cohort 1 is generally similar

to cohort 2 frequency matching will be performed, in which all controls will be selected to get the same distribution according to SVT site and risk factor as cases.

## 4.2 Definition of SVT

### 4.2.1. *Acute Splanchnic vein thrombosis*

Acute splanchnic vein thrombosis is defined as acute symptomatic or acute incidental asymptomatic thrombosis in the mesenteric, splenic, portal or hepatic veins.

Acute symptomatic thrombosis refers to acute onset (< 2 week existent) of symptoms characteristic for SVT thrombosis (including but not limited to abdominal pain) with SVT confirmed with DUS, CTA or MRA, dependent on the anatomical location. Acute incidental asymptomatic thrombosis refers to an incidentally detected SVT with DUS, CTA or MRA, absent on previous diagnostic tests performed in the last 2 weeks before the new incidental finding, in patients without symptoms characteristic of SVT.

The diagnosis of SVT can be made with DUS, CTA and MRA. The diagnosis SVT is defined as the absence of flow in the involved vein (mesenteric, splenic, portal or hepatic vein) as well as the hyperechogenic thrombus inside the lumen seen on DUS. Acute SVT on CTA is defined as a non-enhancing filling defect in the lumen of the involved vein and possibly increased enhancement of hepatic ischemic areas during the arterial phase and decreased enhancement in portal phase. At MR imaging, acute SVT is isointense on T1-weighted images and hyperintense on T2-weighted images.[1]

DUS is the current first line imaging test of choice for the diagnosis of PVT and BCS. However, when DUS is inconclusive MRA/MRP or CTA serves as reference test for the diagnosis of both PVT and BCS. For the diagnosis of SpVT, DUS is the first choice imaging test, however in a non-diagnostic test result, contrast enhanced CT will serve as the reference test.

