### 2.3 Acute versus chronic SVT

Acute SVT has a poor short- and long-term prognosis [24] and a worse survival rate than usual site VTE (lower extremity deep vein thrombosis and/or pulmonary embolism).[9] Therefore, a timely diagnosis is crucial, in order to establish the appropriate anticoagulant treatment. Every manifestation of SVT has a risk of potentially life-threatening thrombotic complications, such as the development of bowel ischemia and the risk of hemorrhagic complications.[1] BCS has a high mortality rate of 10% at 6 months, 13% at 1 year and 18% at 2 years.[25] In one-third of the patients with acute MVT intestinal ischemia is reported and has a mortality rate of 20% at 30 days.[26] Usually, depending on the site of thrombosis, anticoagulant treatment should be started as soon as

possible after diagnosis to prevent progressive and/or recurrent thrombosis. The 2012 guidelines of the American College of Chest Physicians (ACCP) indeed recommend anticoagulation in all patients with symptomatic SVT.[27]

Importantly, since many patients with SVT are at high risk of bleeding, some SVT patients are not treated with anticoagulants. In one study, 25% of the patients with acute PVT or SpVT suffered gastrointestinal bleeding shortly after initiation of anticoagulant therapy, mainly from gastrosophageal varices due to portal hypertension.[9] As a consequence, the ACCP guidelines suggest no anticoagulation in patients with asymptomatic, incidentally detected SVT.[27] However, it is often challenging to diagnose acute SVT as neither of the current available imaging tests is helpful in determination of the age of the thrombus or its clinical relevance. A clear differentiation between acute or chronic thrombotic is therefore often impossible. With an ever increasing incidence of incidentally detected SVT due to the extensive use of CT imaging, especially in patients with liver cirrhosis or solid cancer, the lack of a decisive diagnostic test to differentiate acute from chronic SVT is clearly an unmet clinical need.[3] This illustrates the relevance of the current research proposal.

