## **5.2 Inclusion criteria**

1. Patients with confirmed acute SVT; definitions provided in paragraph 4.2 (Cases, group 1)
2. Patients with confirmed non-symptomatic chronic SVT defined by incident SVT with chronic thrombi on 2 serial imaging tests with at least 3 months interval (controls, group 2)
3. Aged 18 years and older
4. Willing and able to give informed consent

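### Symptomatic cases need recent symptoms and imaging-confirmed SVT but no evidence that the thrombus is new, so an old thrombus can meet the group 1 wording and lower observed sensitivity

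*Combined protocol and SAP*

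**What the plan says.** Section 4.2.1 gives two routes into group 1.

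- **Symptomatic route.** "Acute symptomatic thrombosis refers to acute onset (< 2 week existent) of symptoms characteristic for SVT thrombosis (including but not limited to abdominal pain", and the same sentence goes on to require imaging: "with SVT confirmed with DUS, CTA or MRA, dependent on the anatomical location".
- **Incidental route.** The thrombus must have been "absent on previous diagnostic tests performed in the last 2 weeks before the new incidental finding".

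The confirming criteria in 4.2.1 differ in what they say about age. For DUS the criterion is for SVT in general: "The diagnosis SVT is defined as the absence of flow in the involved vein", plus visible thrombus. For CTA, "Acute SVT on CTA is defined as a non-enhancing filling defect in the lumen of the involved vein"; the perfusion signs are listed only as possible. Only MR has a signal pattern tied to acute disease: "At MR imaging, acute SVT is isointense on T1-weighted images and hyperintense on T2-weighted images".

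On dating by imaging, section 2.3 says that "neither of the current available imaging tests is helpful in determination of the age of the thrombus or its clinical relevance". Section 1 and the synopsis background say the same.

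Section 4.2.2 defines chronic SVT by chronic thrombi on two imaging tests at least 3 months apart, with no condition on symptoms. Section 5.2 adds one for the controls: "Patients with confirmed non-symptomatic chronic SVT". The four exclusions in 5.3 do not include known or previous SVT.

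Under 7.2.1, sensitivity is the share of group 1 scans read as positive for acute SVT, and a point estimate above 90% is acceptable for starting a management study.

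**The concern.** In the symptomatic route, symptom onset is the only explicit evidence of thrombus age. Section 2.1 names abdominal pain as the most frequent symptom and describes the others as nonspecific. Section 4.1 deliberately enrols oncologic, post-surgical and inflammatory or infectious patients, in whom such pain may plausibly have another cause.

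Take a patient with a thrombus documented four months ago who now has a week of abdominal pain and the same thrombus on imaging. The 4.2.1 wording for group 1 can be met. The chronic definition in 4.2.2 can be met too. Only the non-symptomatic condition in 5.2 keeps this patient out of group 2.

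If MRDTI separates old from new clot as the protocol hypothesises, this scan should show no signs of acute SVT. In group 1 that correct reading counts as a false negative. The error falls on the estimate that carries the go criterion, and a test that discriminates better is penalised more.

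**Working it through.** **Inputs.** n = 35 per group (7.1). Exact 95% CI and go criterion above 90% (7.2.1). Sensitivity (Se) 95% and specificity (Sp) 100% from the study of recurrent versus residual leg thrombosis, and Sp 91% as the lower value, both in 2.4.1. The number k of old thrombi in group 1 is **assumed**, from 0 to 4; the documents give no figure.

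**The plan's own precision figure.** Section 7.1 states about ±15%. The exact (Clopper-Pearson) interval for 32/35 = 91.4% is 76.9% to 98.2%, a lower arm of 14.5 points. At 90% it is 75.1% to 97.5%, a lower arm of 14.9 points. The stated figure reproduces as the distance to the lower limit.

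**Go criterion in counts.** 31/35 = 88.6% fails and 32/35 = 91.4% passes, so at least 32 positive readings are needed.

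**Loss per patient.** Expected observed sensitivity = [(35 − k)·Se + k·(1 − Sp)]/35. Each added old thrombus lowers it by (Se + Sp − 1)/35:

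- Sp 100%: 0.95/35 = 2.7 points
- Sp 91%: 0.86/35 = 2.5 points

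The bias is downward whenever Se + Sp exceeds 1.

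**Chance of at least 32/35.** The positives are the sum of Bin(35 − k, Se) and Bin(k, 1 − Sp). For k = 2 and Sp = 100%, at least 32 of the 33 true acute cases must read positive: 0.95^33 + 33 × 0.05 × 0.95^32 = 0.184 + 0.320 = 0.504. With Se = 95%:

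| k | Expected, Sp 100% | P(≥32/35) | Expected, Sp 91% | P(≥32/35) |
|---|---|---|---|---|
| 0 | 95.0% | 90.4% | 95.0% | 90.4% |
| 1 | 92.3% | 75.9% | 92.5% | 77.3% |
| 2 | 89.6% | 50.4% | 90.1% | 55.1% |
| 3 | 86.9% | 19.4% | 87.6% | 28.0% |
| 4 | 84.1% | 0% | 85.2% | 7.9% |

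With k = 4 and Sp = 100%, at most 31 readings can be positive.

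**Other true sensitivities, k = 0 against k = 2.** At Se = 97% (the lower end of the synopsis range for leg DVT) the chance falls from 98.0% to 74.0-77.2%. At Se = 90% it falls from 53.1% to 14.4-18.1%.

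**The case against.** **The two routes differ for a reason.** A symptomatic case has an onset that can be dated; an incidental case does not, so 4.2.1 asks for earlier imaging instead. The synopsis says dating is hard especially in non-symptomatic patients. This explains the asymmetry, but onset dates the symptoms and not the clot.

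**There are other safeguards.** Group 1 requires confirmed acute SVT, and 4.4 requires a final diagnosis before inclusion. A natural reading of 4.2.2 and 5.2 is that the example patient is chronic but symptomatic and belongs to neither group. A sensible investigator may well decide so. However, 4.4 gives no rule for thrombus age, and nothing says that 4.2.1 and 4.2.2 exclude each other. The MR pattern helps only where MR is used, and 2.4.2 reports that pattern from two small studies in which the acute versus chronic distinction was not validated.

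**Stronger readings that the documents do not support.** A reader might infer:

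- that cases qualify on symptoms alone. They do not, because the same sentence requires SVT on imaging.
- that such patients will enter group 1. The text shows only that they can meet its wording.
- that an estimate of 90% or less ends the programme. Section 7.2.1 says what is acceptable for going ahead and states no stopping rule, and the study is described as exploratory.
- that the table predicts the bias in this trial. It does not, since k is assumed.

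**Conclusion.** The gap is real and worth closing. The symptomatic definition requires a recent onset and a thrombus on imaging but no evidence that the thrombus is new, and it overlaps with the chronic definition. The direction of bias is downward if MRDTI discriminates. The size is about 2.5 to 2.7 points of sensitivity per old thrombus among 35. At true sensitivity 95%, two such patients reduce the chance of meeting the go criterion from 90% to about 50-55%.

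This rests on three assumptions: the number of such patients, which the documents do not give; accuracy figures carried over from leg DVT; and old thrombi reading negative at the stated specificity. On the last, 2.4.1 reports that the leg signal had disappeared in all patients after six months. A thrombus only somewhat older than 2 weeks might still read positive and would then do less harm to the estimate.

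**What to change.** Three changes, using only imaging that already exists.

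1. **Make 4.2.1 and 4.2.2 mutually exclusive.** State that a symptomatic patient does not count as a group 1 case if the most recent available imaging from more than 2 weeks before symptom onset already shows thrombus in the same vein segment, unless current imaging documents new or extended thrombus compared with it. The exception, and the reliance on the most recent earlier imaging, keep true same-segment recurrence and acute-on-chronic thrombosis eligible.
2. **Record on the CRF**, for each symptomatic case, whether earlier imaging of that segment exists, its date and its result.
3. **Pre-specify a supporting sensitivity estimate** with exact 95% CI in cases with documented new thrombus: thrombus-free earlier imaging within a stated recency window, or documented extension. Report it beside the primary estimate.

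The cost is one eligibility sentence, a short CRF item and one extra estimate. A few patients with a known, unchanged earlier thrombus would no longer be eligible as cases. The supporting estimate has a smaller denominator and hence a wider interval. Old thrombi that were never imaged before are not caught by change 1 and are addressed only by change 3.

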## 2. Background and rationale

### 2.1 Epidemiology of splanchnic vein thrombosis

Splanchnic vein thrombosis (SVT) includes portal vein thrombosis (PVT), mesenteric vein thrombosis (MVT), splenic vein thrombosis (SpVT) and the Budd-Chiari syndrome (BCS). SVT is underdiagnosed,

given the heterogeneous clinical presentations and the non-negligible rate of asymptomatic incidental findings.[1] In a retrospective review of computed tomography (CT) scans of the abdomen performed for reasons other than the search for suspected SVT, the prevalence of unsuspected abdominal vein thrombosis was 1.7%.[7] Furthermore, 18-30% of the patients with SVT are incidentally detected.[8, 9]

PVT is the most frequent manifestation of SVT, with a yearly incidence of 3.8 cases in males and 1.7 cases in females per 100.000 individuals.[1] BCS is the least frequent manifestation of SVT with a gender-specific incidence of 2.0 cases and 2.2 cases per million individuals, respectively.[1] MVT has an incidence of 2.7 per 100,000 persons per year, with a peak incidence in the age category 70–79 years.[3] There are no precise data available on the incidence of SpVT, other than a 10% prevalence among patients with pancreatitis.[3]

The diagnosis of SVT is often difficult to establish due to the anatomical heterogeneity, with different clinical manifestations according to the site of thrombosis.[3] Abdominal pain is the most frequent symptom and is reported in 60% of the patients with MVT or BCS, and in 40% of the patients with PVT. Hypersplenism, thrombocytopenia, ascites and portal hypertension are frequently reported in PVT and BCS. Other nonspecific symptoms include fever, nausea or vomiting, diarrhea and anorexia.[9]

In at least one-third of the patients with SVT a precipitating risk factor is identified, which include liver cirrhosis, inflammatory, infectious and autoimmune diseases, abdominal surgery, malignancy, inherited and acquired thrombophilia, pregnancy-post-partum periods, hormonal therapy, JAK2 positive myeloproliferative neoplasms (MPN) and paroxysmal nocturnal hemoglobinuria (PNH).[10] The leading cause of BCS is myeloproliferative neoplasm (MPN). In 50% of the patients with BCS a MPN is reported.[11] In patients with PVT, abdominal cancer (gastrointestinal, pancreatic and hepatobiliary system) and liver cirrhosis were the most commonly reported acquired risk factors. Isolated SpVT is most commonly associated with underlying acute pancreatitis.[12]

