### *2.2.2. Doppler ultrasonography*

Doppler ultrasound (DUS) is the current imaging of choice for the diagnosis of PVT and BCS. Previous studies evaluating the accuracy of DUS for the diagnosis of PVT compared to angiographic or surgical-pathologic findings, found a sensitivity of 89-93% and specificity of 92-99%. [13, 14]

In BCS, DUS is usually the first choice imaging, since it is very accurate when performed by an experienced technician.[1] In a small study, a sensitivity of DUS for the diagnosis of BCS of 87,5% was found. The diagnosis of BCS was confirmed by histopathologic findings or by cavography with hepatic vein catheterisation.[15] However in a recent study, contrast enhanced US is found to be more accurate than colour DUS for the diagnosis of PVT and BCS in patients with cancer, with a sensitivity and specificity of >90% and 100%, respectively.[16] For the diagnosis of MVT DUS showed good specificity of 100% at cost of low sensitivity of 79-90%, due to operator-dependent differences. Overlying bowel gas can hinder the visualization of mesenteric veins and make it impossible to visualize the smaller mesenteric vessels.[5] DUS is usually a first-line non-invasive diagnostic test in

SpVT. However, the location of the splenic vein is a disadvantage for DUS, since collateral veins near the splenic hilum can be confused with the splenic vein.

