### *2.2.3. CT angiography*

In the diagnosis of PVT CT angiography compared to intraoperative findings as gold standard, showed a sensitivity of 90% and a specificity of 99%. Furthermore, CT and MR are superior to DUS for providing information about the cause of thrombosis, such as infection, inflammation and cancer.

CT and MR are confirmatory diagnostic tests when DUS is non diagnostic in patients with a clinical suspicion of BCS. Furthermore, CT and MR are superior for assessing the liver perfusion and liver parenchyma and showing indirect signs of BCS (hypertrophy of caudate lobe) and causes for secondary BCS.

For the diagnosis of MVT, CTA and MRA are considered the diagnostic tests of choice. They are more sensitive than DUS, since visualization of mesenteric veins with DUS is often very challenging. Furthermore, the advantage of CT over DUS is the ability to visualise the mesentery and the bowel walls, since thickening of the bowel wall is the most common sign of intestinal infarction due to MVT. Previous small studies evaluating diagnostic accuracy of MVT compared to angiography, intraoperative findings or autopsy found a sensitivity and specificity of 91-91% and 94-100%, respectively.

SpVT is most commonly diagnosed by abdominal contrast-enhanced CT, since SpVT is usually an incidental finding in the evaluation of patients with complicated pancreatic disorders or pre-operative patients with chronic pancreatitis, the two most common situations that accompany SpVT. For the diagnosis of SpVT, dynamic contrast-enhanced CT showed a sensitivity of 71% compared to angiography.

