## **5. Subjects**

### **5.1 Population base**

Consecutive patients with confirmed acute symptomatic SVT, who fulfil all the inclusion criteria and meet none of the exclusion criteria, are eligible for inclusion, as are patients with confirmed chronic

SVT. It is planned to enrol 73-75 subjects in the Rhea study (see paragraph 8.1 for detailed sample size considerations).

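### The negative test that makes an incidental SVT acute has no required modality or vein coverage, so a missed older thrombus can enter group 1 and would tend to lower sensitivity

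*Combined protocol and SAP*

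**What the plan says.** Section 4.2.1 recognises two kinds of acute SVT. Symptomatic cases are dated by symptom onset. Incidental cases have no symptoms, and are defined as an "incidentally detected SVT with DUS, CTA or MRA, absent on previous diagnostic tests performed in the last 2 weeks before the new incidental finding". DUS, CTA and MRA are named for the test that finds the thrombus, but nothing is specified for the earlier test.

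Section 5.2 brings both kinds into group 1: "Patients with confirmed acute SVT; definitions provided in paragraph 4.2 (Cases, group 1"). Section 5.1 describes the cases more narrowly: "Consecutive patients with confirmed acute symptomatic SVT, who fulfil all the inclusion criteria".

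On test accuracy, section 2.2.2 reports that DUS for portal vein thrombosis "found a sensitivity of 89-93% and specificity of 92-99"%, and that for mesenteric vein thrombosis it has "low sensitivity of 79-90%, due to operator-dependent differences". Section 2.2.3 states: "For the diagnosis of SpVT, dynamic contrast-enhanced CT showed a sensitivity of 71% compared to angiography".

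Under section 7.2.1, sensitivity is the share of confirmed acute cases whose scan is read as positive. A point estimate above 90% is the only stated criterion for going on to a management study.

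**The concern.** For a patient without symptoms, the earlier negative test is the main evidence that the thrombus is new. The rest of the plan does not make up for a weak earlier test:

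- The CTA criterion in 4.2.1 is a filling defect. The perfusion signs are only possible additions, so no marker of age is required.
- Section 4.2.1 gives MR signal appearances for acute SVT, but section 2.4.2 says the small studies suggesting them did not validate the acute/chronic distinction.
- Section 2.3 says current imaging does not help to establish the age of a thrombus.
- Controls need two tests at least 3 months apart (4.2.2). Incidental cases have no comparable safeguard.

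A false-negative ultrasound followed within 2 weeks by a CTA that shows an older thrombus therefore meets the rule for group 1. If MRDTI correctly reads that thrombus as not acute, the patient counts against sensitivity. Incidental SVT is the problem the synopsis says the study is meant to solve, so the reference label is weakest where the result matters most.

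**Working it through.** **1. The decision threshold.** 31/35 = 88.6% and 32/35 = 91.4%, so a point estimate above 90% means at least 32 positives of 35. The plan's own precision figure, about ±15% (7.1), can be checked here: the exact 95% interval for 32/35 is 76.9% to 98.2%, with a lower arm of 14.5 points and an upper arm of 6.8. The stated figure reproduces as the lower arm only.

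**2. Miss rates from the protocol (1 - sensitivity).**

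| Test and site | Sensitivity | Missed | Source |
|---|---|---|---|
| DUS, portal | 89-93% | 7-11% | 2.2.2 |
| DUS, Budd-Chiari | 87.5% | 12.5% | 2.2.2 |
| DUS, mesenteric | 79-90% | 10-21% | 2.2.2 |
| CT, portal | 90% | 10% | 2.2.3 |
| CT, splenic | 71% | 29% | 2.2.3 |
| MRA, SVT overall | 90-100% | 0-10% | Synopsis |

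These are the chances that a thrombus already present is not seen. They are not the share of incidental cases that are old.

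**3. Why that share cannot be derived.** It depends on how many truly new thrombi form within 2 weeks in patients imaged twice, and the documents do not give this. The nearest figure is in 2.1, where on CT done for other reasons "the prevalence of unsuspected abdominal vein thrombosis was 1.7"%. Assume, for illustration, that all of these are old and splanchnic. Then

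share old = 0.017 × miss / (0.017 × miss + 0.983 × new).

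| Assumed 2-week rate of new SVT | Miss 7% | Miss 29% |
|---|---|---|
| 0.1% | 55% | 83% |
| 1% | 11% | 33% |
| 5% | 2% | 9% |

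For example, at 7% and 0.1%: 0.00119 / (0.00119 + 0.000983) = 0.55. A range of 2% to 83% is not an estimate.

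**4. What a given number of mislabelled patients would do.** Let m of the 35 cases be old thrombi that MRDTI reads as negative. Take a true sensitivity of 95%, the leg-DVT value in 2.4.1.

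- Expected observed sensitivity = 0.95 × (35 - m)/35.
- Chance of meeting the criterion = P(X ≥ 32), with X binomial (35 - m, 0.95).

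| m | Expected sensitivity | Chance of at least 32/35 |
|---|---|---|
| 0 | 95.0% | 0.904 |
| 1 | 92.3% | 0.759 |
| 2 | 89.6% | 0.504 |
| 3 | 86.9% | 0.194 |

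The values of m are chosen, not derived.

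**The case against.** The strongest reply is that the documents do not show the problem to be large, or even to occur.

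- **Non-diagnostic ultrasound.** A test that did not show the vein does not show absence. Section 4.2.1 also sends inconclusive DUS of portal, hepatic and splenic veins to another modality for diagnosis. This stands: the route into group 1 is a false-negative test, not a non-diagnostic one. The escalation rule does not help there, because a false-negative test does not look inconclusive.
- **Incidental cases may be few.** Section 5.1, read literally, admits none. A reader might apply the 18-30% incidental share in 2.1 and infer 6 to 10 of 35 patients. That share describes all SVT, whereas an incidental patient without a negative test in the previous 2 weeks does not qualify. The documents do not support the count.
- **Signal loss is needed.** In leg DVT the MRDTI signal had gone in all patients after six months (2.4.1). A missed thrombus a few weeks old may still read positive and would not lower sensitivity. This stands, so the downward bias is a tendency that depends on thrombus age.
- **The error is conservative.** It makes the go criterion harder to meet. That is true, but it could wrongly stop a useful technique.

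A reader might also infer that 7-29% of group 1, or of its incidental cases, is old. Those figures are miss rates pooled over different tests and sites, and they leave out MRA.

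**Conclusion.** The gap in 4.2.1 is real: the earlier negative test is limited to a 2-week window and by nothing else. A missed older thrombus can therefore satisfy the definition of acute incidental SVT. If it has lost its MRDTI signal, a correct reading counts as a false negative and tends to lower the primary estimate.

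The size is unknown. It depends on the number of incidental cases in group 1, the share with a false-negative earlier test, and the age of those thrombi; the documents give none of these. What can be said is that the criterion is sensitive to very few patients: under the assumptions in the last table, one mislabelled patient takes the chance of passing from 0.90 to 0.76, and two take it to 0.50. The documents do not support the stronger statement that old thrombi do enter group 1, or in any stated number. The point merits a cheap clarification before recruitment.

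**What to change.** 1. In 4.2.1, require that the earlier negative test adequately visualised the vein segment now found thrombosed, and that it was either the same modality as the detecting test or one at least as sensitive for that site. Record both in the eCRF. State the order of modalities for each site, since section 2.2 gives no figure for some pairs, such as DUS for splenic vein thrombosis.
2. Reconcile 5.1 (acute symptomatic cases only) with 4.2.1 and 5.2 (incidental cases allowed).
3. In 7.2.1, pre-specify sensitivity with exact intervals separately for symptomatic and incidental cases. Add a sensitivity analysis that excludes incidental cases whose earlier negative test was a different and less sensitive modality than the detecting test. State which estimate the 90% criterion uses.

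The cost is a short addition to 4.2.1, an eligibility entry in the eCRF and two extra estimates, using clinical imaging already performed. Somewhat fewer incidental cases will qualify, and the incidental estimate will be imprecise. Misclassification is reduced, not removed: CT followed by CT can still miss a splenic thrombus the first time, and DUS followed by DUS remains operator-dependent.

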## **2.4 Magnetic Resonance Direct Thrombus Imaging as a Promising Alternative**

### *2.4.1. MRDTI for the lower extremity*

Magnetic Resonance Direct Thrombus Imaging (MRDTI) has been shown to be a highly accurate diagnostic method for a first deep vein thrombosis of the legs.[28, 29] The method is based on measurement of the T1 signal which shortens as a result of the formation of methemoglobin in a fresh thrombus.[30] This technique does not require the administration of gadolinium contrast and the acquisition time is short, making it a safe and patient-friendly test. MRDTI was found to have a high sensitivity of 95% and specificity of 91% for a first venography proven symptomatic DVT of the legs [31]. Moreover, interobserver agreement was excellent with a kappa-statistic of 0.89-0.98. A second study found even higher diagnostic accuracy with a sensitivity of 95% and a specificity of

100% [32]. Moreover, the positive signal disappeared in all patients after a period of six months.[32] In the subsequently performed Return-study, it was shown that MRDTI differentiated accurately between patients with confirmed recurrent ipsilateral DVT and those with asymptomatic residual intravascular clots and a normal D-dimer level with a sensitivity of 95% (95%CI 83-99) and a specificity of 100% (95%CI 92-100). This study additionally confirmed the high interobserver agreement with a kappa-value of 0.98.[28]

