#### *2.4.2. MRDTI for splanchnic vein thrombosis*

Only few reports are available on non-contrast enhanced MRDTI for diagnosis of SVT. In one small study evaluating non-contrast and gadolinium enhanced MR imaging for diagnosis of BCS results suggested that MR imaging may be a useful diagnostic modality for detection and classification (acute versus subacute/chronic) of BCS, but correlation with the gold standard (histopathologic findings) was missing.[33] Moreover, two small and outdated studies suggested that in acute SVT and PVT, the clot may be detected inside the lumen of the veins as isointense material on T1-weighted images and hyperintense material on T2-weighted images.[34, 35] However, in both studies the gold standard for SVT/PVT diagnosis was lacking and the differentiation between acute versus chronic thrombus was not validated.

With MRDTI shown to be a valuable diagnostic test for arm vein thrombosis and sinus thrombosis in recent studies, the investigators hypothesize that MRDTI will also prove to be an accurate diagnostic test for acute SVT and for the distinction between acute and chronic SVT since formation of methemoglobin in a thrombus is common to all venous thromboses.[36, 37]

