### **4.3. MRDTI**

MRDTI will be performed as described before with a 1.5 or 3.0 Tesla unit using a T1-weighted magnetisation prepared three-dimensional gradient-echo sequence. The sequence includes a water-only excitation radiofrequency pulse to abolish the fat signal, and the effective inversion time is chosen to nullify the blood signal. Imaging will be performed of the affected veins in two imaging blocks with a total acquisition time of 8-12 minutes by using a 55-cm body coil.

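### Does the T1/T2 signal description of acute SVT in section 4.2.1 select cases on the signal that MRDTI reads?

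*Combined protocol and SAP*

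**What the plan says.** Inclusion criterion 1 (section 5.2) takes the case definition from section 4.2: "Patients with confirmed acute SVT; definitions provided in paragraph 4.2 (Cases, group 1". Section 4.2.1 sets acuteness by time. Either characteristic symptoms have lasted under 2 weeks, or the thrombosis is an incidental finding that was absent on tests in the preceding 2 weeks. In both situations DUS, CTA or MRA shows that SVT is present.

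The section then goes through the tests. DUS requires absent flow and visible thrombus. For CTA, "Acute SVT on CTA is defined as a non-enhancing filling defect in the lumen of the involved vein". For MR, "At MR imaging, acute SVT is isointense on T1-weighted images and hyperintense on T2-weighted images". No flow or luminal finding is stated for MR.

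On which test is the reference, "when DUS is inconclusive MRA/MRP or CTA serves as reference test for the diagnosis of both PVT and BCS". For splenic vein thrombosis DUS comes first and, "in a non-diagnostic test result, contrast enhanced CT will serve as the reference test".

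The index test is acquired "using a T1-weighted magnetisation prepared three-dimensional gradient-echo sequence" (section 4.3). Its principle is given in section 2.4.1: "The method is based on measurement of the T1 signal which shortens as a result of the formation of methemoglobin in a fresh thrombus". Section 7.2.1 computes sensitivity among patients with confirmed acute SVT and accepts a point estimate above 90% as grounds for a later management study.

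**The concern.** A diagnostic accuracy study should not admit cases on the property that the index test measures. Here the only MR appearance given for acute SVT is a T1/T2 signal pattern, it stands in the section that the inclusion criteria make operative, and the index test is T1-weighted. Reading MRDTI blind to the diagnosis (section 4.1) and keeping it out of the treatment decision (section 4.4) would not undo selection at entry.

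The background adds to the unease. Of two small studies that reported the same pattern, section 2.4.2 says that "in both studies the gold standard for SVT/PVT diagnosis was lacking and the differentiation between acute versus chronic thrombus was not validated". Sections 1 and 2.3 say that current imaging does not help to date a thrombus.

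Sensitivity is at stake, and it alone carries the stated criterion for going on to a management study.

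**Working it through.** **The plan's own figure.** With 35 cases (section 7.1), 31/35 = 88.6% does not exceed 90% and 32/35 = 91.4% does, so the criterion needs at least 32 positive readings. The exact (Clopper-Pearson) 95% interval for 32/35 is 76.9% to 98.2%. Its lower arm is 91.4 − 76.9 = 14.5 points, which agrees with the stated precision of about ±15% if that is read as the lower arm. The concern does not touch this figure.

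**The passages side by side.**

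| Question | What the protocol gives |
|---|---|
| What makes a case acute? | Time rules (4.2.1) |
| What does imaging establish? | That SVT is present, by DUS, CTA or MRA (4.2.1) |
| Which MR test is the reference? | MRA/MRP (4.2.1); section 2.2.4 describes contrast-enhanced MRA as showing patency and flow direction |
| What is the status of the T1/T2 sentence? | It speaks of MR imaging in general and lacks the defining verb used for DUS and CTA |
| Can current imaging date a thrombus? | No (sections 1 and 2.3) |

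Authors who hold that imaging cannot date a thrombus are unlikely to have meant a signal pattern as an entry test for acuteness. The descriptive reading fits the whole text; the restrictive reading fits one sentence.

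**Who could be affected.** Only cases confirmed by MR: portal vein thrombosis and Budd-Chiari syndrome after inconclusive DUS, and then only where MRA/MRP is used instead of CTA. Splenic vein thrombosis goes to CT. For mesenteric vein thrombosis, section 2.2.4 says that MR is usually done when CTA is contra-indicated.

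**Which way a bias would go.** Section 4.2.1 describes clot that is isointense on T1. MRDTI looks for T1 shortening, on a sequence that suppresses fat and nulls blood (section 4.3). The documents do not say how clot that is isointense on conventional T1 appears on that sequence, so selection could raise sensitivity, lower it or leave it unchanged.

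**Illustrative size.** Let m cases be MR-confirmed with MRDTI sensitivity s, and let the other 35 − m have sensitivity b. With X ~ Bin(35 − m, b) and Y ~ Bin(m, s) independent, the chance of meeting the criterion is P(X + Y ≥ 32). All three inputs are assumptions; section 7.1 says only that sensitivity is expected to exceed 90%.

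| m, s | b = 90% | b = 93% | b = 95% | b = 97% |
|---|---|---|---|---|
| m = 0 | 53.1% | 77.3% | 90.4% | 98.0% |
| m = 2, s = 70% | 44.1% | 67.0% | 82.0% | 93.7% |
| m = 2, s = 100% | 57.7% | 80.3% | 91.9% | 98.3% |
| m = 5, s = 70% | 31.9% | 50.5% | 65.0% | 79.6% |
| m = 5, s = 100% | 64.7% | 84.5% | 93.9% | 98.8% |

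The largest shift from m = 0 is 77.3 − 67.0 = 10.3 points with two such cases and 77.3 − 50.5 = 26.8 points with five. Moving b from 90% to 97% with no such cases shifts it by 98.0 − 53.1 = 44.9 points. The table shows what the assumed values would do; it does not show that any of them applies here.

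**The case for a change.** The strongest case for acting is that section 5.2 makes section 4.2 binding, that a site confirming a case by MR finds only a signal criterion there, and that nothing says the criterion is not to be used. The route is real: at least five patients each with portal vein thrombosis and Budd-Chiari syndrome are required (section 4.1), and MRA/MRP is a named reference test for both. A clarifying sentence would cost almost nothing.

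Two parts of this stand. Section 4.2.1 does not say whether signal counts for eligibility, and it gives no luminal or flow finding for MRA/MRP. Reader blinding would not repair selection at entry, had it occurred.

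The rest does not carry. The step from missing detail to biased sensitivity needs the sentence to be applied as a criterion, enough cases to be confirmed by MR, and a link between conventional T1 isointensity and the MRDTI reading. The documents establish none of these.

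Nor is there a contradiction with section 2.4.2. That section comments on two particular studies, whereas section 4.2.1 cites a review, and the documents do not show that the review rests on those studies.

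An extra sensitivity estimate without the MR-only cases would not settle the matter. For portal vein thrombosis and Budd-Chiari syndrome those cases follow an inconclusive ultrasound, so leaving them out also changes the site mix and the difficulty of imaging. A difference could not be put down to T1 signal. If signal is not used for entry, there is no such selection to detect.

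**Conclusion.** The concern does not call for a change. Section 4.2.1 leaves a small gap: it describes how acute SVT looks on MR without saying how MRA/MRP confirms it. The timing rules decide acuteness, and a radiologist reporting MRA will judge patency and flow in the ordinary way, so the gap is one that is filled sensibly in practice.

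The effect on sensitivity is zero if no case is confirmed by MR or if signal is not used to classify patients. Otherwise its direction is unknown and its size depends on counts that the documents do not give; under the assumptions above, two MR-confirmed cases move the chance of reaching 32/35 by at most 10.3 points. The sample size, the primary analysis and the >90% criterion are unaffected.

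This conclusion rests on reading the MR sentence as descriptive. Evidence that sites had accepted or refused cases on T1/T2 signal would reopen the question.
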